4.1 Primary Objective

The primary objective of the study is to estimate the proportion of CS patients who are satisfied with their overall symptom control, 6 months after initiating treatment with telotristat ethyl (XERMELO).

4.2 Secondary Objective

The following secondary objectives will be assessed 6 months after initiating treatment with telotristat ethyl (XERMELO):

- To estimate the proportion of patients reporting satisfaction of CS-related diarrhea control
- To estimate proportion of patients reporting satisfaction of CS- related flushing control
- To estimate the proportion of patients reporting reduction in rescue SSA use
- To estimate the proportion of patients reporting reduction in the dose of long-acting SSA injection
- To estimate the proportion of patients reporting reduction in the frequency of long-acting SSA injection
- To estimate the proportion of patients reporting an overall improvement in CS control after initiating XERMELO based on patient global impression of change (PGIC)
- To estimate the proportion of patients that had reduction in in work-related absenteeism, presenteeism, activity impairment, and overall productivity loss after initiating XERMELO based on Worker Productivity and Activity Impairment: Specific Health Problem v2.0 (WPAI- SHP)
- To estimate the proportion of patients reporting weight gain

4.3 Exploratory Objective(s)

5. Investigational Plan

5.1 Overall Study Design

In this study, the 2 specialty pharmacies, tasked with distributing XERMELO to patients, will be responsible for the identification and recruitment of patients. All eligible patients initiating treatment with XERMELO will be invited to participate in this study.

Individuals assigned by the specialty pharmacies (the ‘site staff’) will be responsible for describing the study to patients. An initial verbal consent will be obtained to collect personal contact information and to share it with the [REDACTED] and/or Research Triangle Institute (RTI) (collectively, the ‘study team’) for the purpose of providing additional information about the study, collecting informed consent, and managing access and/or support for the web-based survey.

The specialty pharmacies will send contact information to the study team, for patients who express interest in participation, via an approved method of communication noting the patient's unique specialty pharmacy identification (ID) number, first name, phone number, electronic mail (e-mail) address, and preferred time of contact (eg, morning, mid-day, evening). For patients who do not provide consent for further contact, the specialty pharmacies will be asked to provide aggregate data to the study team including patient(s) age, sex, geographic region, insurance type, reason for refusal to participate, and total number of patients who refused to provide consent.

As this study will be completed via an online survey and patients are to complete the enrollment process independently, electronic consent will be utilized for this study. Enrollment will be self-directed through a unique survey link sent directly to the patient's e-mail address. Each patient receiving an invitation to the survey will be assigned a numerical patient ID code; the patient ID will be assigned by the study team, based on a subject ID log at each specialty pharmacy. If successful enrollment is not logged within 30 days of the initial survey e-mail invitation or within 14 days of the subsequent survey e-mail invitations, the study team will make up to 3 attempts to contact the patient via e-mail and/or telephone to complete the enrollment process for study participation. The enrollment process and Baseline survey may be completed anytime within the 30-day window, at a time convenient for the patient.

If the study team is unsuccessful in reaching the patient, the patient will be considered lost-to-follow up and the study team will update the enrollment status as appropriate.

Upon completion of the electronic consent and successful enrollment, the patient will be prompted to complete an online survey at Baseline, then every 6 months for a period of up to 3 years. All surveys will be completed online, at the patient's convenience, and in accordance with [Appendix A](#). The study team will provide technical support and reminder prompts, as described above, throughout the duration of participation.

At any time after Baseline, if the study team is unable to reach a patient after 3 attempts and the patient does not complete the survey within the prespecified window, the patient will be considered lost-to-follow up and the study team will disable the patient's unique study link as appropriate. Awareness by the specialty pharmacy of any change in the patient's status (ie, withdrawal of consent, treatment discontinuation) must be communicated to the study team. Should the specialty pharmacy communicate a patient's status change during the 3-year Follow-up Period, the study team will disable the patient's unique study link upon notification and no further survey invitations or reminders will be triggered.

Information regarding a patient's initial prescription and refill(s) will also be collected from the specialty pharmacies for all enrolled patients.

5.1.1 Survey Conduct

An electronic consent and survey questionnaire approved by an Institutional Review Board (IRB) will be used by RTI to program the online survey for the purpose of standardizing responses among patients.

Each patient will complete up to 7 web-based surveys over the duration of the study. Each survey is anticipated to take no more than 20 minutes on average.

All assessments, except mortality, will be patient-reported; medical records will not routinely be requested or reviewed as part of this observational study unless required for safety reporting purposes. As patient recall over time may be limited, partial responses as in the case of dates of onset, and/or estimates of numerical information will be accepted.

Participation in the study is contingent on continued use of XERMELO. Each survey will establish ongoing treatment with XERMELO and continued consent to study participation prior to subsequent data collection.

The initial survey is intended to gather Baseline information, which may include:

- Sociodemographics (age, year of birth, sex, race, ethnicity, education, geographic region)
- Current medical history as it relates to CS, NET burden, NET location, and related conditions
 - Location of NET
 - Date of diagnosis; CS and NET
 - CS-related hospitalization(s)
 - CS-related ER visit(s)
 - NET-related surgery (eg, tumor debulking, lysis of adhesions)
- Satisfaction with CS, CS-related diarrhea and/or flushing control prior to starting XERMELO, where applicable
- Height and weight
- Concomitant medication as it relates to the following:
 - Long-acting SSA therapy

- Use of rescue medication - short-acting SSA
- Systemic tumor-directed therapy
- Liver-directed therapy (eg, chemoembolization)
- WPAI-SHP

The initial survey should be completed no later than 30 days, and subsequent surveys should be completed no later than 14 days, after the unique survey link has been provided to the patient via e-mail. Patients will be asked to complete a survey every 6 months for up to 3 years. The following patient-reported data may be collected as described in [Appendix A](#):

- Satisfaction with CS, CS-related diarrhea and/or flushing control after initiating XERMELO, where applicable
- PGIC
- Concomitant medication as it relates to the following:
 - Change in use of rescue medication - short-acting SSA
 - Change in long-acting SSA therapy
 - Systemic tumor-directed therapy
 - Liver-directed therapy (eg, chemoembolization)
- Change in weight
- WPAI-SHP
- Incidence of CS-related hospitalization(s)
- Incidence of CS-related ER visit(s)

The incidence of mortality will be tracked indirectly based upon information received by RTI through secondary sources of information (eg, available pharmacy records).

6. Study Population

This observational, noninterventional, single-arm study will include patients with CS and who are initiating treatment with XERMELO.

The recruitment period was anticipated to be approximately 18 months from first patient enrolled; however, due to slow enrollment, the recruitment period has been extended to 6 months before data collection end. Each patient will be followed for up to 3 years; the last patient enrolled will be eligible to complete a Baseline survey and the first 6 month survey.

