10.3 Study Endpoints

10.3.1 Primary and Secondary Endpoints

The primary study endpoint is the proportion of CS patients who are satisfied with their overall symptom control, 6 months after initiation of treatment with telotristat ethyl (XERMELO).

Secondary endpoints include the following outcomes, assessed at 6 months among patients with CS after initiation of treatment with telotristat ethyl (XERMELO):

- Proportion of patients reporting satisfaction of CS-related diarrhea control
- Proportion of patients reporting satisfaction of CS-related flushing control

- Proportion of patients reporting reduction in rescue SSA use
- Proportion of patients reporting reduction in the dose of long-acting SSA injection
- Proportion of patients reporting reduction in the frequency of long-acting SSA injection
- Proportion of patients reporting an overall improvement in CS control after initiating XERMELO based on PGIC
- Proportion of patients that had improvement reduction in work-related absenteeism, presenteeism activity impairment, and overall productivity loss after initiating XERMELO based on WPAI- SHP
- Proportion of patients reporting weight gain

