2.4 Sample Size Determination

The sample size was derived by satisfying design assumptions for the primary study endpoint of the proportion of patients with CS who are satisfied with their overall symptom control, 6 months after initiating treatment with telotristat ethyl (XERMELO). Of specific interest is the proportion of patients with CS who are at least somewhat satisfied with their control of CS at 6 months, defined as those patients with a response of either "very satisfied" or "somewhat satisfied". This proportion will be estimated as x/n , where x is the number of patients in the study who are either "Very satisfied" or "Somewhat satisfied", and n is the number of patients with a non-missing response for the primary endpoint. Two-sided 95% confidence limits (CLs) will be calculated for this proportion using normal approximation. The true proportion may be approximately 50%; hence, an expected proportion of 50% was used in the sample size calculation as it requires the largest n . It is desired for the proportion to be known with a precision, ω , of 5%, that is, for the CLs to be $(x/n) \pm \omega$. Based on the expected proportion of 50% and the precision requirement of 5%, $n = 385$ patients are needed to have a non-missing response for the primary endpoint. Assuming that 40% of the patients who participate in the study will drop out prior to the 6-month survey, then a minimum of $N = 643$ patients, with CS who initiate treatment with XERMELO, should be entered into the study.

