3.2.5 Work Productivity and Activity Impairment Questionnaire—Specific Health Problem (WPAI-SHP)

The WPAI-SHP is a self-administered questionnaire ([Reilly et al., 1993](#)) comprising 6 questions that measure the effect of health problems on participants' ability to work and participate in regular activities based on their experiences in the previous 7 days. This questionnaire will be administered at Baseline and at the initial 6-month Follow-up.

The WPAI-SHP includes 4 domains (absenteeism, presenteeism, work productivity loss, and activity impairment). All participants will be asked whether they are employed (Q1) and how their CS-related problems affected their regular activities (Q6). Employed participants will be asked about hours of work missed due to CS-related problems (Q2), hours of work missed for any reason (eg, vacation, holidays, time off to participate in this study) (Q3), hours actually worked (Q4), and the degree that CS affected their productivity while working (Q5). An integer scale from 0 to 10 is used for Q5 and Q6, where 0 corresponds to no effect and 10 corresponds to complete effect.

Responses to the items are scored to produce the following 4 domains:

- Absenteeism: work time missed due to CS = [REDACTED]
- Presenteeism: impairment while working due to CS = [REDACTED]

- Work productivity loss: overall work impairment due to CS = [REDACTED]
[REDACTED]
- Activity impairment: activity impairment due to CS = [REDACTED]

Each score is then multiplied by 100 to express domains in terms of impairment percentages, with higher numbers indicating greater impairment and less productivity (ie, worse outcomes).

3.2.6 *Carcinoid Syndrome-related Health Care Resource Utilization*

At Baseline and at each Follow-up, questionnaire items will ask patients about ER visits and hospitalizations during the prior 6-month period. Data collected will include the following:

- The number of ER visits and the CS-related reason for each visit
- The number of hospitalizations, the number of nights for each stay, and the CS-related reason for each hospitalization

3.2.7 *Study Discontinuation and Mortality*

Patients will be terminated from the study if they discontinue the use of XERMELO, withdraw consent for participation, or are lost to follow-up. Information on reasons for discontinuation will be provided by the specialty pharmacy.

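### The primary proportion is framed for patients 6 months after starting XERMELO, but the main estimate covers only survey respondents still taking it

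*Protocol*

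**What the plan says.** **Target.** Protocol 4.1 sets out to "estimate the proportion of CS patients who are satisfied with their overall symptom control, 6 months after initiating treatment". Protocol 10.3.1 says the same of the endpoint: "The primary study endpoint is the proportion of CS patients who are satisfied with their overall symptom control, 6 months after initiation of treatment". SAP 2.2.1 and 2.3.1 agree. None of these limits the target to patients still on treatment.

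**Removal of stoppers.** Protocol 5.1.1 states "Participation in the study is contingent on continued use of XERMELO" and adds "Each survey will establish ongoing treatment with XERMELO and continued consent to study participation prior to subsequent data collection". Under Protocol 5.1 the pharmacies report treatment discontinuation, and the study team then disables the patient's "unique study link upon notification and no further survey invitations or reminders will be triggered". SAP 3.2.7 says "Patients will be terminated from the study if they discontinue the use of XERMELO".

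**Estimator.** Satisfaction after initiation is asked only at the first 6-month follow-up (SAP 3.2.3). The main estimate is x/n, where "n is the number of patients with a non-missing response for the primary endpoint" (SAP 2.4), and Protocol 10.4.1 rules out imputation in the main analysis. Non-responder imputation (NRI) of the primary endpoint is a planned sensitivity analysis (Protocol 10.4.1, SAP 5.1.4).

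**Related provisions.** The analysis population requires data on at least one primary or secondary endpoint (Protocol 10.2, SAP 5.1.2). The disposition table counts completed questionnaires and gives discontinuations after each follow-up and overall, with reasons (SAP 5.1.3.1). On refills, Protocol 5.1 says: "Information regarding a patient's initial prescription and refill(s) will also be collected from the specialty pharmacies for all enrolled patients". Protocol 6.3 lists the reasons participation ends and does not name stopping treatment.

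**The concern.** The objective names one population and the data collection yields another. A reader of the final report would take the headline as the share of patients starting XERMELO who are satisfied at 6 months. In fact, anyone who stopped before then cannot contribute an answer.

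This differs from ordinary survey non-response because the removal rule is plausibly tied to the outcome. Protocol 3.2 records the sponsor's assumption that satisfied patients stay on the drug. If that is right, those removed are on average less satisfied than those who remain, and x/n is too high for initiators. The confidence interval covers sampling error only and gives no sign of this.

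**Working it through.** **1. The plan's own figures (SAP 2.4).** Expected proportion 0.50, precision 0.05, 95% two-sided, 40% dropout.

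- n = 1.96² × 0.5 × 0.5 / 0.05² = 384.16, rounded up to 385. This matches.
- N = 385 / 0.60 = 641.7, rounded up to 642. The SAP states 643, an immaterial difference.
- Half-width at n = 385: 1.96 × √(0.25/385) = 4.99 points.
- Without a month-6 response: 643 − 385 = 258 (40.1%).

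The arithmetic is sound, but the 5-point precision applies to month-6 respondents only.

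**2. What happens to a patient who stops before month 6.** If the pharmacy reports it, the link is disabled. If it does not, the month-6 survey checks for ongoing treatment before collecting data. If the patient does not complete the survey, Protocol 6.3 classes the patient as lost to follow-up by default. In each case there is no primary response and the patient is not in n.

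**3. Size of the overstatement.** Let d = 0.40 (dropout) and p = 0.50 (satisfied among respondents), both from SAP 2.4. The documents do not give the next three, so they are assumptions: s, the share of dropouts who stopped the drug; q, the proportion of stoppers satisfied; r, the proportion of other dropouts satisfied.

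Overstatement = d × [s(p − q) + (1 − s)(p − r)]

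If other dropouts resemble respondents (r = p), this reduces to d × s × (p − q), in percentage points:

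| q | s = 25% | s = 50% | s = 75% | s = 100% |
|---|---|---|---|---|
| 0% | 5.0 | 10.0 | 15.0 | 20.0 |
| 25% | 2.5 | 5.0 | 7.5 | 10.0 |
| 40% | 1.0 | 2.0 | 3.0 | 4.0 |
| 50% | 0 | 0 | 0 | 0 |

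It exceeds 5 points only if q < 0.5 − 0.125/s. The threshold is 0 at s = 25%, 25% at s = 50%, 33.3% at s = 75% and 37.5% at s = 100%.

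If other dropouts differ from respondents (q = 25%):

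| r | s = 25% | s = 50% | s = 75% |
|---|---|---|---|
| 40% | 5.5 | 7.0 | 8.5 |
| 50% | 2.5 | 5.0 | 7.5 |
| 60% | −0.5 | 3.0 | 6.5 |

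**4. No assumption about dropouts.** Suppose 193 of 385 respondents are satisfied (50.1%). Among all 643 enrolled, the proportion can lie anywhere from 193/643 = 30.0% (NRI; half-width 3.5 points) to (193 + 258)/643 = 70.1% (every dropout satisfied).

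**5. Does the planned NRI reach the stoppers?** The primary and secondary endpoints are all assessed at 6 months. Read literally, the analysis population rule drops a patient with no month-6 data. If all 258 fell out this way, NRI would return 193/385 = 50.1%, the same as the main analysis. Over all enrolled it returns 30.0%. The visible text does not say which denominator applies.

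**The case against.** The strongest reply is that this is a disclosed design choice with safeguards already planned. Protocol 5.1.1 and SAP 3.2.7 state the continued-use condition openly, the SAP introduction calls the study a registry of XERMELO users, and SAP 2.4 defines n as non-missing responses. That stands: restricting to continuing users is legitimate. But the objective, the endpoint and the visible heading in SAP Table 1 keep the initiator wording, so the label is still wrong for the estimate.

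NRI is prespecified, and it would do little if it left out patients without month-6 data, so the sensible reading includes them. The supplemental cell for the primary endpoint in Table 1 is partly redacted and may say so. SAP 4.1.2 also plans a baseline summary of all 643 patients. This reduces the denominator question to a point for clarification. It does not change what the main x/n describes.

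Completed-questionnaire counts will show how many patients were lost before month 6, and the pharmacies supply reasons for discontinuation. True, but the table does not name the Baseline-to-month-6 interval for those reasons, and an unreported stopper can be filed as lost to follow-up.

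The month-6 item asks how XERMELO has controlled symptoms (SAP 3.2.3), so an answer from someone who stopped earlier would be retrospective. This favours relabelling over surveying stoppers.

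Finally, direction and size are assumed. The sponsor's statement about satisfied patients does not prove that stoppers are dissatisfied, and the 30.0% to 70.1% envelope would apply to any survey with this much non-response. Both points are correct and limit the finding accordingly.

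**Conclusion.** The concern holds. As planned, the main x/n estimates satisfaction among survey respondents still taking XERMELO at month 6, while the objective and endpoint are worded for patients who initiated it. An upward difference is likely if satisfied patients tend to continue, but this is an inference.

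The size cannot be determined from the documents. The range of 1 to 20 points rests on p = 50%, d = 40%, s from 25% to 100%, q from 0 to 40%, and other dropouts resembling respondents. It is not a bound: with p = 70%, s = 100% and q = 0, the same formula gives 0.4 × 0.7 = 28 points. Nor is it always material. At p = 50% with r = p, it stays within the planned 5 points when s is 25% or less or when q is 40%, and it vanishes at q = 50%. It turns slightly negative in one of the cases where other dropouts are more satisfied than respondents. This should be fixed because the headline can mislead and the correction is cheap.

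**What to change.** Keep the non-imputed main analysis and make these changes.

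1. **Label.** In tables and conclusions, describe the main x/n as *among survey respondents still taking XERMELO at month 6*, or reword the endpoint to match. Cost: wording only.
2. **NRI and disposition.** State in SAP 5.1.4 that the primary-endpoint NRI uses all enrolled patients, and report it beside the main result as a lower bound. Give Baseline to month 6 its own disposition row, splitting missing month-6 responses into treatment stop, death, withdrawal of consent and survey non-response. Check patients recorded as lost to follow-up against the refill data, using a gap rule fixed beforehand in the variable specification document (SAP 5.1.1). That would give an estimate of s. Cost: one sentence, one row and one derived variable, with no new data collection, though the pharmacy transfer process is still undecided (SAP 2.1, 3.1). If the redacted Table 1 text already sets the denominator at all enrolled, the NRI part reduces to side-by-side reporting.
3. **Optional.** For patients not yet at month 6, keep the satisfaction item open to those who stopped XERMELO without withdrawing consent, and report answers by on-drug and off-drug status. Cost: an amendment with IRB approval, and a mixed cohort.
4. **Reconcile** Protocol 6.3 with Protocol 5.1, 5.1.1 and SAP 3.2.7 on whether stopping treatment ends participation. At present 6.3 reaches it only if noncompliance is read together with the treatment requirement in 7.1. Cost: wording at the next amendment.

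The downsides are modest. A less favourable figure appears beside the headline. NRI counts deaths and all other non-response as not satisfied, so it is only a bound. A refill gap is an imperfect marker of stopping. Extending NRI to diarrhea, flushing and PGIC is optional.

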6.1 Inclusion Criteria

Patients must meet all of the following criteria to be considered eligible to participate in the study:

1. Adult, ≥ 18 years of age at the time of informed consent
2. A new, valid prescription for XERMELO
3. Initiating XERMELO for the treatment of carcinoid syndrome
4. Able and willing to provide informed consent prior to participation in the study

6.2 Exclusion Criteria

Patients who meet any of the following criteria will be excluded from participating in the study:

1. Unable to understand and read English
2. Unable to access the internet
3. Prior exposure to XERMELO

